 - i. Patients provisionally enrolled based on verbal consent
 - ii. Enrollment and official consent are upon initial patient encounter with their PCP
- b. Follow-up from October 1, 2020-September 15, 2024
- c. Index Date (T0)
 - i. Initial Patient Encounter with their PCP (e.g., visit, secure message) following receipt of packet
- d. Follow-up Period – Analyze two time points
 - i. 6 months following the index date (T6)
 - 1. Follow-up survey may be more than six months after the initial visit, depending on when the RAs are able to successfully contact the patient for the follow-up survey
 - ii. 12 months following the index date (T12)

3. **Study Arms**

- a. Study Arm Assignment
 - i. PCPs were randomized upon Academic Detailing session attendance
 - ii. Patients were assigned to a study arm based on their PCP on file upon enrollment
- b. Arm 1 (Control): Academic Detailing + General Packet
- c. Arm 2 (Intervention): Academic Detailing + Patient Pre-Visit Preparation Packet

Statistical Analysis Plan (SAP)

We will construct generalized estimating equation (GEE) models to compare changes from baseline in clinical and patient-reported outcomes ($p < 0.05$) between clinical trial arms. All statistical analyses will use SAS 9.4 (SAS Institute Inc), and regression models were fit using PROC GENMOD. For each deprescribing, patient-reported and hypoglycemia-related outcome, we will construct a regression model with baseline measurements of the outcome included as covariates and a repeated statement to account for patient clustering within PCP panels. We will also examined heterogeneity of treatment effect (HTE) based on demographic and baseline clinical variables by calculating interaction term p-values from the models with and without interaction terms at 6 and 12 months for the deprescribing primary outcome.

The Table lists each baseline covariate that will be used in each outcome model.

Outcome Model	Baseline Covariate(s) Included
Any deprescribing (T6 and T12 models)	On insulin at T0 – y/n and on sulf at T0 – y/n
Self-reported severe hypoglycemia event from T6 patient survey	Self-reported severe hypoglycemia event from T0 patient survey
Hypoglycemia-related ED or IP diagnosis (T6 and T12 models)	Hypoglycemia-related ED or IP diagnosis in 1 year prior to T0
HbA1c lab result (T6 and T12 models)	Latest HbA1c lab result prior to T0 >8%

4. Outcomes

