Outcome	Timepoints	Summary Statistic in Each Arm and At Each Timepoint	Effect Estimate, Difference in:	Initial Statistical Test
HbA1c Value	Baseline, Follow-up	Mean and CI	Means	T-test
HbA1c <=8	Baseline, Follow-up	% of Arm	Proportions	Chi-sq
Hypo IP	Baseline, Follow-up	% of Arm	Proportions	Chi-sq
Hypo ED	Baseline, Follow-up	% of Arm	Proportions	Chi-sq
ED	Baseline, Follow-up	% of Arm	Proportions	Chi-sq
IP	Baseline, Follow-up	% of Arm	Proportions	Chi-sq
PCP Visits	Baseline, Follow-up	% of Arm	Proportions	Chi-sq
Survey Responses	Baseline, Follow-up	% of Arm	Proportions	Chi-sq
PEPPI Scores	Baseline, Follow-up	Mean and CI	Means	T-test
PAID5 Scores	Baseline, Follow-up	Mean and CI	Means	T-test
RAND PSQ	Follow-up	% of Arm	Proportions	Chi-sq

a. Primary Outcomes

- i. Deprescribing of either insulin or SU
 - 1. Discontinuation of either insulin or SU
 - 2. Reduction in dose of insulin or SU
 - 3. Switch from a higher risk to lower risk version of insulin
- ii. Timeframe for determining baseline and follow-up medication regimen
 - 1. Single-date regimen at T0, T6, and T12

b. Secondary Outcomes

- i. Changes in HbA1c levels
 - 1. Baseline HbA1c: Use most recent prior to T0 in the year prior to T0; if no HbA1c in year prior to T0, pull forward eligibility HbA1c
 - 2. Follow-up T6: in this timeframe, pick the HbA1c closest to T6
 - 3. Follow-up T12: in this timeframe, pick the HbA1c closest to T12?
- ii. Hypoglycemic-related hospitalizations
- iii. Hypoglycemic-related ED visits
 - 1. Number of hypoglycemic-related ED visits between T0-T6

c. Patient-reported outcomes (Change between baseline and follow-up questionnaires)

- i. Incidence of patient-reported moderate and severe hypoglycemic events
- ii. Less diabetes-related stress
- iii. Perceived quality of care

5. **Baseline data**

- a. PCP Data
- b. Patient Data
 - i. Demographics: Race, Ethnicity, Age, Gender, Language
 - ii. Patient Engagement: Kp.org status, Kp.org usage
 - iii. Comorbidities Data lookback: 1 year before study visit date
 - iv. Clinical Characteristics
 - 1. Medications: Diabetes Medication Regime (Insulin, Sulfonylurea), Medication Count (All Medications)
 - 2. Labs: HbA1c
 - a. Data lookback: 1 year before study visit date
 - b. HbA1c Selection: most recent one prior to T0
 - 3. Hypoglycemic-related hospitalizations
 - 4. Hypoglycemic-related ED Visits
 - v. Membership/Insurance
 - vi. Baseline Survey Responses

6. **Lost to Follow-up**

- a. Reasons

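### The single HbA1c row in the covariate table does not name its outcome, and on either reading the continuous HbA1c outcome has no listed adjustment for its own baseline value

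*Combined protocol and SAP*

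**What the plan says.** In the Statistical Analysis Plan section, the covariate table is introduced with "The Table lists each baseline covariate that will be used in each outcome model". Its only HbA1c row is "HbA1c lab result (T6 and T12 models"), and the only covariate beside it is "Latest HbA1c lab result prior to T0 >8"%. The row gives no scale, distribution or link. The section opens with a general intention to use GEE models to "compare changes from baseline in clinical and patient-reported outcomes".

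The outcome table in section 4 has two HbA1c rows: HbA1c Value (means, t-test) and HbA1c <=8 (proportions, chi-square). The tests stand in a column headed "Initial Statistical Test". Section 4.b.i names the secondary outcome as "Changes in HbA1c levels", and 4.b.i.1 defines its baseline as a selected laboratory value: "Use most recent prior to T0 in the year prior to T0; if no HbA1c in year prior to T0, pull forward eligibility HbA1c". Section 1.b.i sets the entry limit at 8% or below.

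**The concern.** HbA1c is the plan's measure of whether glycemic control moves when insulin or sulfonylurea is reduced. Its own baseline value is the obvious covariate, and the plan already selects that value. Yet the only HbA1c covariate listed is a yes/no split at the limit that patients had to meet to enter. It can be positive only for patients whose latest result before T0 differs from the eligibility result and exceeds 8%, so it probably separates few patients and says nothing about differences at or below 8%.

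At stake are the precision of a secondary comparison, protection against chance baseline imbalance, and clarity about which HbA1c model is the planned one. As written, an analyst could fit the value, the change or the binary outcome to the same row.

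**Working it through.** The plan gives no figure to reproduce. The check has two parts.

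**1. The two readings side by side.**

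- *Row models HbA1c <=8.* This fits the other three rows, which pair yes/no outcomes with yes/no baselines. The >8% indicator is that outcome's own baseline status. In simulation (correlations 0.3-0.7, 2-25% above 8%), using the indicator instead of the continuous baseline changed the standard error (SE) by -2% to +3%, which is not material. But no row then covers HbA1c Value. The opening GEE sentence includes clinical outcomes in general and names no covariate for it.
- *Row models the value or its change.* The only covariate is the indicator. In a change-score model the baseline value is subtracted, but with a fixed weight of one. In a follow-up-value model, differences at or below 8% go unadjusted.

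Neither reading lists a model for the continuous outcome with the baseline value as covariate.

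**2. What the indicator costs under the second reading (illustration).** Assumed inputs, none from the documents:

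- q, the share above 8%: 0-16%
- r, the baseline to follow-up correlation: 0.3-0.7
- a roughly normal baseline
- s, baseline SD divided by follow-up SD: 1 or 0.8
- clustering ignored

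Share of baseline variance carried by the indicator: k = phi(z_q)^2 / [q(1-q)]. This gives k = 0 at q = 0 (the covariate is then constant), 0.224 at 5% and 0.440 at 16%.

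With follow-up variance set to 1, residual variance with the continuous baseline is 1 - r^2 for either form of the outcome. With the indicator it is 1 - r^2 k for the value and (r - s)^2 (1 - k) + 1 - r^2 for the change. The SE ratio is the square root of indicator over continuous:

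| Model | q | r = 0.3 | r = 0.5 | r = 0.7 |
|---|---|---|---|---|
| Follow-up value (any s) | 0 | 1.048 | 1.155 | 1.400 |
| | 5% | 1.038 | 1.122 | 1.321 |
| | 16% | 1.027 | 1.089 | 1.240 |
| Change, s = 1 | 0 | 1.240 | 1.155 | 1.085 |
| | 5% | 1.191 | 1.122 | 1.066 |
| | 16% | 1.141 | 1.089 | 1.048 |
| Change, s = 0.8 | 0 | 1.129 | 1.058 | 1.010 |
| | 5% | 1.101 | 1.046 | 1.008 |
| | 16% | 1.074 | 1.033 | 1.005 |

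Worked cells: value, r = 0.7, q = 16%: sqrt[(1 - 0.49 x 0.440)/0.51] = sqrt(0.7844/0.51) = 1.240. Change, s = 0.8, r = 0.5, q = 0: sqrt[(0.09 + 0.75)/0.75] = 1.058. When s = r, for example both 0.7, the term (r - s)^2 vanishes and the change score loses nothing.

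Imbalance: if patients at or below 8% differ between arms by 0.1 percentage point at baseline and s = 1, the arm difference shifts by 0.1r = 0.03 to 0.07 point in a value model and by -0.1(1 - r) = -0.07 to -0.03 in a change-score model. These shifts also depend on s.

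**The case against.** The strongest reply is that the binary reading is the likelier one, and that it removes the covariate problem for the outcome the row describes. That stands: the SE losses above belong to the less likely reading. It is also possible that >8% is a misplaced part of the outcome label, which would again make the row binary. Neither point supplies a baseline covariate for HbA1c Value.

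A second reply is that the table also omits PAID5, PEPPI, RAND PSQ, all-cause ED and inpatient use, and PCP visits, so a missing row is nothing special to HbA1c. That is partly right. But the sentence on baseline adjustment covers patient-reported outcomes without a row, while HbA1c is a named secondary outcome that depends on its row.

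Two stronger readings are tempting, and the documents do not support them:

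- *The row breaks the SAP's own rule.* A reader might infer this from "baseline measurements of the outcome included as covariates". The full sentence applies to deprescribing, patient-reported and hypoglycemia-related outcomes. HbA1c is not among them, so preferring a continuous baseline is a matter of good practice and not of internal contradiction.
- *HbA1c Value will be tested only by a t-test that ignores PCP clustering.* The t-test is labelled as initial, and the opening GEE sentence reaches clinical outcomes, so it cannot be taken as the final inference.

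Finally, the entry limit applies at baseline and not at follow-up, so the baseline SD may well be the smaller one. This objection stands: the equal-SD change-score losses are not a floor.

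**Conclusion.** The point holds as a cheap improvement to one secondary outcome, of minor severity. The row leaves its outcome unnamed, and the continuous HbA1c outcome has no listed model with its baseline value as covariate. If the row is binary, nothing material is lost for HbA1c <=8 and the gap is one of specification for the value. If it is continuous, a follow-up-value model has an SE about 3-5% larger at r = 0.3 and 9-40% larger at r = 0.5-0.7; the top end needs r = 0.7 and nobody above 8%. A change score loses 5-15% at r = 0.5-0.7 with equal SDs, about 1-6% at an SD ratio of 0.8, and possibly nothing. All of these rest on assumed correlations, SD ratios and shares above 8%.

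A reader might infer that the weak covariate biases the arm comparison. It does not: assignment is randomized, and what suffers is precision and the handling of chance imbalance. The primary deprescribing analysis is unaffected.

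**What to change.** Name the outcome in the existing row. Add a row for HbA1c value in per cent (T6 and T12 GEE models, clustered by PCP) whose covariate is the latest HbA1c value before T0, continuous, selected by 4.b.i.1. Keep the >8% indicator as the baseline for HbA1c <=8. With the continuous baseline in a linear model, analyzing the value or its change gives the same arm estimate and SE, so that choice no longer matters.

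The cost is one or two lines in the table; 4.b.i.1 and 5.b.iv.2 already call for the data. The drawback is timing. The plan is dated 12/2/2024 (revised 3/6/2025), follow-up ended on September 15, 2024, and the SAP refers to model fitting partly in the past tense, so the change may be post hoc. Record it as a dated amendment and, if results by arm have been seen, report both versions.

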2. **Patient pre-visit preparation** is a more patient-centric strategy that has shown efficacy for improving clinical interactions and shared decision making. In this strategy, patients are prepared for clinical encounters prior to visits. Information exchange is bi-directional (i.e., patients receive information about relevant trade-offs and provide information about preferences and other relevant information to facilitate collaborative decision making with their provider).

The study has the following aims and design:

Aim 1: To compare academic detailing alone (Arm 1) to academic detailing + patient pre-visit preparation (Arm 2). We will measure differences in medication de-prescribing rates among well-controlled older patients with type 2 diabetes at high risk for medication-related hypoglycemia. [primary clinical outcome]

Aim 2: To compare differences between these 2 arms in patient-reported diabetes distress, decisional confidence, and perceived quality of care. [primary patient-reported outcomes]

Protocol Summary

Importance: Medication-related hypoglycemia is the leading cause of iatrogenic complications among older adults with type 2 diabetes (T2D).

Objective: Compare two strategies for insulin and/or sulfonylureas deprescribing in older patients with T2D treated in a PCP-randomized clinical trial (RCT).

Interventions: PCPs will 1+ academic detailing (AD) sessions that provide evidence to support diabetes medication reassessment and potential deprescribing strategies in older patients with T2D. Prior to their visit with a participating PCP, trial patients will be randomly assigned to receive either a pre-visit deprescribing activation handout or an attention control healthy lifestyle handout.

Main Outcomes and Measures: Primary outcomes (assessed at 6 months) are diabetes medication deprescribing (an aggregate measure) and any patient-reported severe hypoglycemia episodes.

Protocol Details

1. **RCT Eligible Participants**

- a. Kaiser Permanente members aged 75+ years with Diabetes Type 2
- b. Inclusions:
 - i. Hemoglobin A1c<=8% (in-control)
 - ii. Current use (in prior six months) of insulin and/or sulfonylurea
 - iii. Consent to participate in the study
- c. Exclusions:
 - i. Deceased
 - ii. End of KP Membership
 - iii. Does not speak English
 - iv. Medical exclusions (Type 1 diabetes, cognitively impaired, palliative care, chemo regime)

2. **Study period**

- a. Patients provisionally enrolled from October 1, 2020-July 31, 2023

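### Does the primary outcome need a netting rule for patients in whom one target drug is cut while the other is started or raised?

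*Combined protocol and SAP*

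**What the plan says.** Section 4.a.i defines the primary clinical outcome as "Deprescribing of either insulin or SU" and lists three ways to meet it: "Discontinuation of either insulin or SU", "Reduction in dose of insulin or SU" and "Switch from a higher risk to lower risk version of insulin". Section 4.a.ii fixes how the regimen is read: "Single-date regimen at T0, T6, and T12".

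The Protocol Summary describes the outcome as an aggregate measure and does not explain the aggregation. The covariate table in the Statistical Analysis Plan models it as any deprescribing at T6 and at T12, adjusted for whether the patient was on insulin and on an SU at T0.

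Eligibility (section 1.b) admits users of insulin, an SU or both. Section 9 lists sensitivity analyses for missing data, visit modality and prior hypoglycemic events. The outcomes grid at the head of section 4 has no deprescribing row, and section 8.d names an outcomes table without giving its contents.

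**The concern.** The components are joined by "either" or "or", so one is enough. A single-drug user can stop that drug and start the other, and a dual user can have one reduced and the other raised. Both score as events, exactly like a patient who drops a drug with nothing put in its place. The only switch the definition mentions is within insulin; movement between insulin and SU is not discussed. The T0 covariates describe the starting regimen and cannot pick up a later start or increase.

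Aim 1 compares deprescribing rates between arms, and the trial's rationale is medication-related hypoglycemia. If an appreciable share of events were exchanges of one target drug for the other, and more so in one arm, the comparison would say less about reduced exposure than it appears to. Severe hypoglycemia, hypoglycemia-related ED or inpatient diagnoses and HbA1c reflect consequences. They do not show what the deprescribing count is made of.

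**Working it through.** **Can the case arise under the rule?** Give each drug three levels (none, lower dose, higher dose) at T0 and at follow-up, and require at least one drug at T0.

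- Transitions: 9 × 9 = 81, less 9 that start on neither drug = 72.
- No drop in either drug: 6 × 6 = 36, less the same 9 = 27. Transitions with a drop: 72 − 27 = 45.
- One drug down and the other up: 3 × 3 × 2 = 18.

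So 18 of the 45 qualifying patterns are offset. These are logical patterns, not patients. They show that the case is possible, not that it is common. Within-insulin switches are left out of this grid.

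**What would it do to the arm comparison?** Keep the denominator and let the offset rate be the percentage of all patients in an arm who count as events but also had the other drug started or raised. Then

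net risk difference = counted risk difference − (offset rate in Arm 2 − offset rate in Arm 1).

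This is an identity and needs no assumption. The documents give no deprescribing rate, offset rate or sample size, so the figures below rest on assumed counted rates of 20% in Arm 1 and 28% in Arm 2. The counted odds ratio is (0.28/0.72)/(0.20/0.80) = 1.56.

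| Offset rate, Arm 1 / Arm 2 (points) | Net rates | Risk difference (points) | Odds ratio |
|---|---|---|---|
| 0 / 0 | 20% / 28% | 8.0 | 1.56 |
| 1 / 1 | 19% / 27% | 8.0 | 1.58 |
| 2 / 2 | 18% / 26% | 8.0 | 1.60 |
| 4 / 4 | 16% / 24% | 8.0 | 1.66 |
| 1 / 2 | 19% / 26% | 7.0 | 1.50 |
| 2 / 1 | 18% / 27% | 9.0 | 1.69 |
| 1 / 4 | 19% / 24% | 5.0 | 1.35 |
| 4 / 1 | 16% / 27% | 11.0 | 1.94 |

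Equal offset rates leave the risk difference alone and move the odds ratio slightly away from 1, so in that case the literal count is the more cautious one. For the difference to vanish, Arm 2 must exceed Arm 1 by the full 8 points. With no offsets in Arm 1, that is 8/28 = 29% of Arm 2's events.

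A variant assumes that the same share q of events is offset in each arm. The risk difference then shrinks by the factor 1 − q and the risk ratio does not change. With assumed rates of 20% and 30%, q from 5% to 20% gives 10.0 × 0.95 = 9.5 down to 10.0 × 0.80 = 8.0 points, and the ratio stays at 1.5.

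**What would a netted analysis need?** It needs a threshold for a dose increase. If a move to a lower-risk insulin is to be checked for a rise in total dose, it also needs doses that compare across insulin versions. The documents supply neither.

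**When would it be added?** Follow-up ended on September 15, 2024. The plan is dated 12/2/2024, 78 days later, and was revised on 3/6/2025, 172 days later. It already states that "regression models were fit using PROC GENMOD", although the sentences around that phrase are mostly in the future tense.

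**The case for a change.** The best case for a change is that this is a primary outcome and its text does not mention the offset patient. One programmer could score that patient as an event under the literal wording. Another could read the word aggregate as meaning net and score a non-event. The T0, T6 and T12 regimens should already hold both drugs, so one sentence and a count by arm would cost little, and only such a count can show whether the issue is empty.

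Part of this stands. No stated rule or named analysis deals with the case, and the size is unknown until someone counts. The ambiguity is thinner than it looks, though. The either/or components and the any-deprescribing label already classify the patient, and aggregate most naturally means a pooling of the listed components. A sentence in 4.a.i would restate the rule that is there. The count is a descriptive line the analysts can produce from planned data whenever they wish, and neither the primary model nor its interpretation as written depends on it. A netted re-analysis would be post hoc and crude: a patient whose SU is stopped and whose insulin rises just past the chosen threshold would become a non-event. It would answer a different question from the one in Aim 1.

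**Conclusion.** The observation about the text is right, but the plan does not need to change. An any-component composite is a fair way to measure whether prescribers acted on insulin or an SU. It fits the stated objective of deprescribing one or both, and it can be applied as written. Its cost is that the count does not separate a reduction with no offset from an exchange.

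No bias between arms is shown. The effect on the risk difference equals the arm gap in offset rates: zero if the rates are equal, and one point for each point of gap. In the illustration a 3-point gap moves an 8.0-point difference to 5.0 or 11.0. That rests on assumed rates, and nothing in the documents points to a gap in either direction. The conclusion assumes that the program follows the literal wording of 4.a.i. If it nets offsetting changes, the report's outcome definition should say so, which is ordinary reporting practice. It makes no judgement on which medication change is appropriate for any patient.

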COVER PAGE

Title: Reducing Treatment Risk in Older Patients With Diabetes: Comparative Effectiveness of Academic Detailing With and Without Pre-Visit Patient Preparation

ClinicalTrials.Gov Registration: NCT04585191

12/2/2024 (revised 3/6/2025)

RETRO RCT Analytic Plan

Background

Over one-quarter of people aged 65 and older have type 2 diabetes, and this proportion is expected to increase rapidly in coming decades. Glycemic control in older patients must balance the short-term risks of treatment (e.g., hypoglycemia and its immediate consequences) with the long-term benefits of reduced microvascular complications (e.g., diabetic retinopathy or renal disease). Of increasing concern, hypoglycemia has become the leading preventable complication of treatment in this older population and increases the risk of cognitive decline, falls, lower health-related quality of life, hospitalization, and death. These severe consequences of hypoglycemia begin to change the balance between treatment benefit and risk as patients get older and develop increasing frailty and additional co-morbid chronic conditions. As patients age, they are less likely to experience the long-delayed benefits associated with tight glycemic control and more likely to suffer from the short-term risk of treatment-related hypoglycemia. This changing balance creates a critically important decisional dilemma of how best to balance long-term treatment goals with short-term treatment risks to optimize current health and well-being.

Design and Methods

We will conduct a comparative effectiveness randomized clinical trial involving the following two strategies for changing clinical management, both of which are transportable to a wide range of clinical settings and can be readily adopted into clinical practice:

1. **Academic detailing** is a well-validated strategy for changing prescribing practices that employs focused and pragmatic education for practicing clinicians. Academic detailing sessions are generally brief (30-45 minutes), integrated into the usual workday (e.g. during practice weekly meetings or lunches), and consist of clearly presented summaries of current evidence and guideline recommendations.

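### Acute events are attributed to a cause only in the direction of benefit; the plan has no hyperglycemia-related ED or IP outcome to mirror the hypoglycemia one

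*Combined protocol and SAP*

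**What the plan says.** The Protocol Summary states the objective as "Compare two strategies for insulin and/or sulfonylureas deprescribing in older patients with T2D", and names as primary outcomes "diabetes medication deprescribing (an aggregate measure) and any patient-reported severe hypoglycemia episodes". Section 4.a counts stopping insulin or a sulfonylurea, lowering its dose, or moving to a lower-risk insulin.

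Acute events classified by cause all concern hypoglycemia:

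- Section 4.b lists "Hypoglycemic-related hospitalizations" and ED visits of the same kind, the latter specified as "Number of hypoglycemic-related ED visits between T0-T6".
- The section 4 outcome table has Hypo IP and Hypo ED rows.
- The SAP covariate table has the row "Hypoglycemia-related ED or IP diagnosis (T6 and T12 models"), adjusted for the same diagnosis in the year before T0.
- Section 4.c adds patient-reported moderate and severe hypoglycemia.

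Measures that could register the opposite direction are:

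- HbA1c: change in HbA1c is a secondary outcome, the outcome table has rows for the value and for the proportion at or below 8%, and the covariate table lists T6 and T12 models.
- All-cause ED and all-cause IP: each has an outcome-table row summarised as a percentage of the arm, with a chi-square as the initial test. Neither is among the section 4.b secondary outcomes, and neither has a row in the covariate table.

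Death appears in section 6 as a reason for loss to follow-up, not as an outcome.

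**The concern.** A trial that encourages less glucose-lowering treatment should look for acute events on both sides: those it hopes to prevent and those it might cause. Here an admission for low glucose is identified as such, while an admission for high glucose is one more all-cause admission.

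What is at stake is the reading of a favourable result. If Arm 2 shows more deprescribing and fewer hypoglycemia events, the obvious next question is whether acute hyperglycemia rose in exchange. The planned tables would answer it only indirectly: through a laboratory value, or through visit totals dominated by other causes.

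**Working it through.** **1. Reproducing the plan.** The documents state no sample size, power, effect size or event rate, so there is no figure to reproduce. What can be checked is coverage and, with assumed rates, how much the all-cause rows dilute a specific excess.

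**2. Coverage, side by side.**

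| Measure | Hypoglycemia | Hyperglycemia |
|---|---|---|
| Cause-specific admission | Section 4.b; Hypo IP row | none |
| Cause-specific ED visit | Section 4.b; Hypo ED row | none |
| ED/IP model, T6 and T12 | SAP covariate table | none |
| Patient report | Protocol Summary; section 4.c | none |
| Laboratory measure | – | HbA1c value, HbA1c at or below 8%, T6/T12 models |
| All-cause ED, all-cause IP | mixed in | mixed in |

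**3. Dilution.** Assumptions: two-sided alpha 0.05, 80% power, 1:1 allocation, no clustering. Control-arm risk of a hyperglycemia-related ED/IP event is 0.5% or 1%, with an excess of 1 or 2 points. All-cause visit risk is 20%, 30% or 40%. Each excess event is assumed to add one patient to the all-cause count. That favours the all-cause row, because some of these patients would have had another visit anyway.

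Per-arm size, pooled-variance formula, with p̄ the mean of the two risks:

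n = [1.960·√(2p̄(1−p̄)) + 0.842·√(p₀(1−p₀)+p₁(1−p₁))]² / (p₁−p₀)², rounded up.

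Example, 1% vs 3%: p̄ = 0.02; √0.0392 = 0.1980; √(0.0099+0.0291) = 0.1975. The numerator is about 0.3072, and dividing by 0.0004 gives 768.01, so 769. The same 2 points on a 20% background (20% vs 22%) gives 6,510. Ratio: 6,510/769 = 8.5.

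| Assumed excess | Cause-specific, n per arm | All-cause 20% | All-cause 30% | All-cause 40% | Ratio |
|---|---|---|---|---|---|
| 0.5% → 1.5% | 1,553 | 25,583 | 33,275 | 37,827 | 16.5–24.4 |
| 1% → 2% | 2,319 | 25,583 | 33,275 | 37,827 | 11.0–16.3 |
| 1% → 3% | 769 | 6,510 | 8,394 | 9,493 | 8.5–12.3 |

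**4. What the added outcome could show at moderate size.** At an assumed 250 per arm, power is 36% for 1% vs 3% and 20% for 0.5% vs 1.5%, against 4–8% through all-cause visits (rejection in the harmful direction only). As an estimate, the 95% half-width is 1.96·√{[p₀(1−p₀)+p₁(1−p₁)]/250}:

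- 1% vs 3%: 1.96·√(0.0390/250) = 2.4 points.
- 20% vs 22%: 1.96·√(0.3316/250) = 7.1 points.
- 40% vs 42%: 1.96·√(0.4836/250) = 8.6 points.

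**5. The HbA1c measures.** Under assumed values, a 0.3-point mean difference with SD 0.7 to 1.0 needs n = 2·[SD·(1.960+0.842)/0.3]² = 86 to 175 per arm. HbA1c above 8% in 5% vs 15% needs 141 per arm. Loss of control is therefore far easier to detect by HbA1c than by any event count.

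Clustering by PCP would raise all these sizes and widen all these intervals.

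**The case against.** The case against giving this weight is substantial.

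- **All-cause visits are tabulated.** A reader might infer from the hypoglycemia outcomes that the trial counts no other ED or hospital events. It does: all-cause ED and IP have their own rows. This stands. What those rows lack is any attribution to cause.
- **HbA1c covers the opposite direction.** It is a listed secondary outcome with models at both time points, and step 5 shows it is the more sensitive measure. This stands too. But it is a surrogate, not an acute event, and its follow-up selection rule is unsettled: section 4.b refers to an undefined timeframe, and the T12 rule ends in a question mark.
- **The aims are narrower than benefit-risk.** The Background says "Glycemic control in older patients must balance the short-term risks of treatment", and a reader might conclude that without hyperglycemia events the benefit-risk question cannot be answered. That passage sets short-term treatment risk against long-term microvascular benefit, which no 12-month ED or IP count would settle. Aim 1 is limited to deprescribing: "We will measure differences in medication de-prescribing rates among well-controlled older patients". Aim 2 is patient-reported. No net benefit-risk analysis is planned.
- **A null HbA1c test might be taken as safety.** Nothing in the plan says a non-significant result will be read as preserved control, so this cannot be charged to it. Much of what is wanted is already planned; only a CI on the adjusted arm difference is not stated.
- **Few events.** Both arms receive academic detailing, entry required HbA1c of 8% or less, and type 1 diabetes was excluded. The count may be small and the outcome underpowered. This argues for a descriptive outcome rather than a tested one. It does not argue for leaving it out.

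**Conclusion.** The point holds in a limited form. Acute events are classified by cause only in the direction of benefit. Acute harm from reducing insulin or a sulfonylurea can be seen only through HbA1c and undifferentiated all-cause ED and IP visits.

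The coverage finding rests on the documents alone. The size of the dilution, roughly 8 to 24 times as many patients, rests on the assumed rates; the factor moves with them, but all-cause visits were the weaker route in every scenario tried. The gap does not invalidate the stated aims. Closing it is a cheap improvement to what the trial can report about harm, and would still leave a wide interval.

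**What to change.** Add a safety outcome, *Hyperglycemia-related ED or IP diagnosis*, to section 4.b, the outcome table and the SAP:

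1. Use the same T0-T6 and T0-T12 windows and the same kind of diagnosis data as the hypoglycemia outcome, with the code list written down before arm-level results are examined.
2. Report counts and percentages by arm, and the arm difference with a 95% CI that allows for PCP clustering.
3. Fit the GEE with the prior-year diagnosis as covariate only if event numbers allow it; sparse or empty cells can prevent it from converging.
4. Label the outcome as descriptive and as added after follow-up ended. The cover page dates the plan 12/2/2024, revised 3/6/2025, while section 2 ends follow-up on September 15, 2024.
5. For the HbA1c models already planned, report the adjusted arm difference with its PCP-clustered 95% CI.

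The cost should be one more code list, one table row and one reported interval. This assumes the diagnosis data used for hypoglycemia can be searched for the new codes; the documents do not describe the extract. The downside is few events and a wide interval, so a small count should not be presented as evidence of no harm.
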